Official Title:	Hypnosis for Chronic Pain Relief in Cancer Survivors
NCT number:	03867760
Document Type:	Study Protocol and Statistical Analysis Plan
Date of the Document:	January 28, 2019

RESEARCH PROTOCOL

Methods and Design

Design. The study design is a two-arm RCT. The study uses an expanded protocol from the pilot RCT. The primary outcome (pain intensity) and secondary outcomes (pain interference, anxiety, depression, fatigue, and sleep disturbance) will be assessed at baseline, mid-study, and end of study. In addition, pain intensity and anxiety will be assessed daily. Participants will be randomly assigned to the RHI or an attention control condition (relaxation recording). Furthermore, an extreme phenotype approach will be taken to study brain states as a mechanism for hypnosis-induced pain reduction. Five participants from each group who score low (score = 0 - 1)¹ on the hypnotic suggestibility scale and 5 participants from each group who score high (score = 4 - 5)¹ will be invited to undergo qEEG measurement.

Sample and Settings. A convenience sample of 100 cancer survivors with chronic pain will be recruited from the Seattle Cancer Care Alliance (SCCA) Survivorship Clinic. SCCA is a National Cancer Institute-designated comprehensive cancer center where more than 6,000 patients with cancer received treatment last year. In 2016, 194 patients were seen at the Survivorship Clinic (based on chronic pain prevalence estimate of 39%, 76 patients with pain).

Power Analysis. Table 1 shows the minimal detectable change in the mean of the RHI group that can be detected given a total sample of 100 participants and 80% power, based on standard deviations observed in our prior research.

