Intervention/Independent Variables. *Hypnosis Intervention.* The RHI consists of four 12- 18-minute digital recordings that I will make using standardized hypnosis scripts for pain reduction² and upload to a MP3 player. The scripts were developed for patients with chronic pain and tested by a psychologist who is an expert in hypnosis research ([name], co-mentor). Participants will listen to the recordings daily for 28 days in the prescribed order (4 recordings for 3 days each, and then any recording for the remaining 16 days). Selected recordings will be noted by the participant on the Daily Diary. The script includes an induction, suggestions for how to access inner resources and manage pain, and post-hypnotic suggestions for permanence of hypnosis

Table 1. Minimal Detectable Change in RHI Group

For N=100 (50/group), 80% power, alpha = 0.05, two-sided

Pain Score Standard Deviation		
Small SD (1.0)	Expected SD (1.5)	Large SD (2.0)
-0.57	-0.85	-1.13

benefits and self-hypnosis practice. Attention Control. The relaxation recordings will be uploaded to a MP3 player. Four different 12- 18-minute recordings of the selected genre will be listened to daily for 28 days (same prescribed order as the RHI).

Table 2a. Instruments.

Aim	Study Measures	Variable Measured	Week 0	Daily	Week 2	Week 4
1	*PROMIS 29 v. 1.0 29-item questionnaire, Cronbach's α 0.92-0.97. ³	Pain interference, anxiety, depression, fatigue, sleep	X		X	X
1	*PROMIS v.1.0-Pain Intensity 3a 3-item questionnaire, Cronbach's α 0.92-0.97. ³	Pain intensity	X		X	X
2	*PROMIS Self-Efficacy for Managing Symptoms	Self-Efficacy	X			X
3	qEEG	Brain activity/state	X		X	X

* National Institute of Nursing Research (NINR) Common Data Elements

Table 2b. Instruments.

Aim	Study Measures	Variable Measured	Week 0	Daily	Week 2	Week 4
1	Daily Diary 9-item questionnaire completed at bedtime, feasibility of participants completing it on a daily basis was established in pilot study.	Pain intensity, anxiety, and use of RHI or relaxation recording (including which recording used)		X		
2	Stanford Hypnotic Clinical Scale for Adults 5-item scale, 20 minutes to administer, product-moment correlation between total score and Stanford Hypnotic Scale C total score 0.72. ¹	Hypnotic suggestibility	X			
2	Tellegen Absorption Scale 34-item multi-dimensional scale, ⁴ test-retest reliability 0.85. ⁵	Absorption (Imaginative involvement, tendency to become mentally absorbed)	X			

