2	Credibility/Expectancy Questionnaire 4-item questionnaire, test-retest 0.62-0.78, Cronbach's α 0.84-0.85. ⁶	Treatment outcome expectancy	X			
1	Demographic Questionnaire 15-item questionnaire.	Socio-demographics; cancer & treatment, and pain history; comorbidities; pain interventions	X			
3	Structured Interviews Each interview is anticipated to last 20 minutes and will be audio-recorded.	Barriers and facilitators associated with undergoing qEEG measurement; how intervention works				X

Data Collection Schedule and Procedures. Study Enrollment. The research assistant (RA) will contact potential study participants by telephone to screen, obtain verbal consent, and schedule the Week 0 study visit at the UW HSC. Baseline questionnaires and consent form will be mailed to the participant with instructions to complete 1-2 days before the Week 0 study visit.

Week 0 Study Visit. The RA will meet with the participant to (1) collect completed questionnaires and signed consent form; (2) administer the Stanford Hypnotic Clinical Scale; (3) share group assignment; (4) provide teaching about the RHI or relaxation recording, and participant study responsibilities; (5) administer the Credibility/Expectancy Questionnaire; and (6) inform participant if they are eligible for the qEEG measurement. Participants who are ineligible for the qEEG measurement (or eligible but not interested in participating) will begin using the assigned intervention at home on the same day as the Week 0 visit. The RA will schedule telephone calls with ALL participants to complete study measures at Week 2 (within 5 days of using the assigned intervention for 14 days), and Week 4 (within 5 days of using the assigned intervention for 28 days). Structured interviews with the RA also will be conducted by telephone. Participants will be reminded to return the Daily Diary in the provided pre-posted return envelope. Participants in the qEEG study arm will undergo the first qEEG at the Week 0 visit and begin using the assigned intervention at this time. All qEEG measurements

will take place at the UW Integrative Brain Imaging Center (IBIC). Week 2 and Week 4 qEEGs will be scheduled at the Week 0 visit and will take place within one day of completing study measures.

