questionnaires (\$25) and diary (\$25). Participants also will be given \$25 to pay for parking and gas, or for public transportation for the visit to the UW HSC. The 20 participants undergoing qEEG will receive an additional \$50 after completing each qEEG for a total of \$150. They also will be given \$25 to pay for parking and gas, or for public transportation to the UW IBIC for two visits (\$50). Data will be managed using REDCap (Research Electronic Data Capture).⁹ The RA will be responsible for data entry and I will verify its accuracy.

Data Analysis. *Aim 1: Does the RHI work? Evaluate the efficacy of RHI in reducing self-reported pain intensity (primary outcome) and pain interference, anxiety, depression, fatigue, and sleep disturbance (secondary outcomes) at 4 weeks compared to the attention control condition (relaxation recording).* We will use ANCOVA controlling for baseline scores and co-variates including pharmacologic treatments to test whether *mean pain intensity* at week 4 differs between the RHI and relaxation groups. The same analysis will be done for the secondary outcomes. In addition, we will graphically describe trajectories of daily pain and anxiety at Weeks 0, 2, and 4, based on the Daily Diary for pain intensity and anxiety in the RHI and relaxation groups. This approach will allow us to understand whether an increased dose of the intervention (i.e., 4 weeks vs. 2) is necessary to achieve significant reduction in pain intensity.

Aim 2: For whom does the RHI work? Examine if psychological factors (hypnotic suggestibility, mental absorption, treatment outcome expectancy) moderate the relationship between RHI and pain intensity at weeks 0, 2, and 4. The following multiple regression model will be estimated:

$\text{PAIN}_{\text{week}2} = \text{Pain}_{\text{week}0} + \text{PSY}_{\text{week}0} + \text{RHI} + \text{PSY}_{\text{week}0} \times \text{RHI}$, where moderator effects will be indicated by the interaction term $\text{PSY}_{\text{week}0} \times \text{RHI}$. We will measure Cohen's d for each of the levels of the moderator and compare them to determine the moderator effect. The resulting effect size will be used to estimate the sample size in a larger follow-up study (e.g., R01).

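### The Aim 1 efficacy test uses Week 4 pain alone with no missing-data method, so participants with only a Week 2 score leave it; the Week 4 contrast is biased if that loss depends on Week 2 pain differently by arm

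*Combined protocol and SAP*

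**What the plan says.** The Design paragraph states that the primary and secondary outcomes "will be assessed at baseline, mid-study, and end of study", and Table 2a marks the PROMIS measures at Weeks 0, 2 and 4. Under Week 0 Study Visit: "The RA will schedule telephone calls with ALL participants to complete study measures at Week 2", with a second call at Week 4.

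The Aim 1 test under Data Analysis uses one of the two follow-up times. The method is given as "We will use ANCOVA controlling for baseline scores and co-variates including pharmacologic treatments to test whether", and the sentence closes by asking if the outcome "at week 4 differs between the RHI and relaxation groups". The secondary outcomes get the same analysis. For the diary, "we will graphically describe trajectories of daily pain and anxiety at Weeks 0, 2, and 4, based on the Daily Diary", which is description and not a test.

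Week 2 pain enters a model in two other places. It is the outcome in the Aim 2 moderator equation, and it is used in the Aim 3 cross-sectional mediation analyses, which need qEEG and so cover only the qEEG subset. The documents state no analysis population, no missing-data method and no dropout rate. The Power Analysis paragraph gives the detectable change "given a total sample of 100 participants and 80% power", with no allowance for loss.

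**The concern.** The plan does not use the words complete case. The exclusion follows from the method: an ANCOVA with a single Week 4 outcome cannot include someone who lacks that outcome, and no rule brings them back.

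Loss between the two calls is plausible. The Week 4 call is timed from 28 days of using the recording, so its date is not defined for someone who stops early. Outside the qEEG subset, payment is tied to the baseline questionnaires and the diary, not to that call. Participants are told their assignment, so reasons for leaving could differ between arms.

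If RHI participants whose pain is still high at Week 2 leave, and controls do not leave in the same way, the RHI completers look better at Week 4 than the randomised RHI group would have. The Week 2 score that would adjust for this is already scheduled for everyone. Aim 1 is the trial's only test of efficacy.

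**Working it through.** **1. The plan's own figure.** Table 1 is headed "For N=100 (50/group), 80% power, alpha = 0.05, two-sided". The normal approximation at SD 1.5 is SD × √(2/n) × (1.960 + 0.842) = 1.5 × √(2/50) × 2.802 = 1.5 × 0.2 × 2.802 = 0.84. The noncentral t version gives 0.566, 0.849 and 1.132 for SD 1.0, 1.5 and 2.0, matching the stated 0.57, 0.85 and 1.13. Table 1 therefore holds with 50 analysed per arm and no loss.

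**2. Inputs.** From the documents: 50 per arm, SD 1.5, two-sided alpha 0.05, difference -0.85. Assumed, because the documents do not give them:
- loss after Week 2, mostly 15-30%;
- logistic dependence of loss on Week 2 pain;
- correlations (Weeks 0-2, 2-4, 0-4) of 0.6/0.7/0.5 or 0.5/0.8/0.4, with 0.5/0.7/0.4 and 0.6/0.8/0.5 also tried for the -0.85 case;
- a Week 2 effect half the Week 4 effect when a true effect is present.

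**3. Where the bias comes from.** To first order, bias ≈ b × (selection shift in RHI - selection shift in control). Here b is the slope of Week 4 on Week 2 pain given baseline. The shift is how far completers' mean Week 2 pain, given baseline, lies from that of everyone in their arm. With equal SDs, b = (r24 - r02 × r04) / (1 - r02²):
- 0.6/0.7/0.5: (0.7 - 0.30) / (1 - 0.36) = 0.40/0.64 = 0.625
- 0.5/0.8/0.4: (0.8 - 0.20) / (1 - 0.25) = 0.60/0.75 = 0.80

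Equal shifts in the two arms cancel. With selection in the RHI arm only, a bias of -0.07 needs a shift of about -0.07/0.625 = -0.11 points, and a bias of -0.31 needs about -0.31/0.80 = -0.39.

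**4. Simulation.** Pain scores at the three times were drawn as trivariate normal. The Week 4 ANCOVA in completers was compared with the maximum-likelihood estimate for monotone missing data. That estimate regresses Week 2 on arm and baseline in everyone, and Week 4 on arm, baseline and Week 2 in completers. The Week 4 contrast is then the arm coefficient from the second fit plus its Week 2 coefficient times the arm coefficient from the first. Covariates other than baseline were not simulated.

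| Loss after Week 2 | True effect | Bias, Week 4 ANCOVA | ANCOVA rejects at 5% | Bias, Week 2 used |
|---|---|---|---|---|
| Unrelated to pain, 10-30% | -0.85 | about 0 | not computed | about 0 |
| Same dependence in both arms | none | within 0.02 | 4-7% | within 0.01 |
| Same dependence in both arms | -0.85 | about +0.03 to +0.05 | not computed | about 0.01 or less |
| RHI arm only, 15-30% | none | -0.07 to -0.31 | 6-15% | within 0.01 |
| RHI arm only, 10-30% | -0.85 | -0.08 to -0.22 | not computed | about 0.01 or less |
| Opposite patterns, 20% per arm | none | -0.29 to -0.42 | 17-29% | within 0.01 |

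Relative to 0.85, the RHI-only range under no effect is 0.07/0.85 = 8% to 0.31/0.85 = 36%.

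**5. Sensitivity to the assumptions.** With RHI-only dependence at a log-odds slope of 1 per SD and 15% loss, bias is -0.08 to -0.12 and rejection 6-8%. At 5-10% loss it is -0.005 to -0.13 with rejection 4.5-7%. Bias near -0.3 takes about 30% loss and a slope of at least 1.5 per SD.

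**6. Precision.** With 20% random loss, using Week 2 lowers the SD of the estimate from 0.305 to 0.293, or from 0.293 to 0.280, depending on the correlations.

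**The case against.** Both arms use four recordings of the same length, daily for 28 days, in the same order. Leaving for lack of benefit could therefore work the same way in both, and then the Week 4 ANCOVA shows no false-positive inflation and is slightly conservative at a true effect. This stands, and it limits the point. A reader might infer that the plan will declare efficacy that is not there. The documents do not support that: it needs a dropout mechanism that differs by arm, and they give neither a dropout rate nor evidence of such a difference. The opposite-patterns case also requires low-pain controls to leave, for which no reason appears.

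Three other strong readings fail:
- That the ANCOVA is unbiased only if leaving depends on arm and baseline alone. Under no effect, equal dependence on Week 2 pain in both arms leaves the contrast essentially unbiased.
- That Week 2 pain is thrown away. It is unused only in the Aim 1 test.
- That stopping the recordings removes a participant. Week 4 measures are taken by telephone, and someone who stops listening but completes the call stays in.

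It is also fair that a baseline-adjusted Week 4 comparison targets the stated aim directly. The weakness lies in the silence on missing Week 4 scores, not in the choice of Week 4.

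**Conclusion.** The point holds in conditional form and should be addressed. As written, a participant with a Week 2 but no Week 4 score has no route into the efficacy test. Whether this matters depends on how many are lost and whether the link between Week 2 pain and leaving differs by arm. At plausible but assumed loss of 15-30%, the result ranges from practically no bias (same mechanism) to about a third of the 0.85 detectable difference in favour of RHI (dependence in the RHI arm only). Opposite patterns mark an outer bound and are not an expectation. Using Week 2 removes the bias in these scenarios because leaving was made to depend only on observed data; loss driven by pain after Week 2 would bias that analysis too. The case rests on protection against bias, since the precision gain is small.

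**What to change.** Make the primary analysis a likelihood-based repeated-measures model of Week 2 and Week 4 pain intensity with arm, week, arm-by-week, baseline pain, baseline-by-week, the planned covariates and an unstructured covariance. Include all randomised participants with any post-baseline score, in their assigned arm, and name the Week 4 arm contrast as the primary test. The baseline-by-week term is needed for the model to match the estimate checked above, which fits a separate baseline slope at each week. Keeping the Week 4 ANCOVA with multiple imputation that includes Week 2 pain is an equivalent route.

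Treat the secondary outcomes the same way. Keep the complete-case Week 4 ANCOVA as a sensitivity analysis, and add a missing-not-at-random sensitivity analysis. Fix the choice before outcome data are seen by arm.

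The cost is SAP wording, slightly more analysis work and reliance on missing at random for the primary result. With complete data, the Week 4 contrast is essentially the planned ANCOVA.

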Aim 3: How does the RHI work? Compare brain states as measured by qEEG in cancer survivors with chronic pain receiving the RHI relative to the attention control condition (relaxation recording) at weeks 0, 2, and 4. We will use multiple regression models controlling for baseline scores and co-variates (e.g., medication use) to compare the change in theta activity from *pre-session* to *during session* between RHI and relaxation groups. We will also compare the change in theta activity from *pre-session* to *post-session* between groups. This will be replicated for all 3 time points: Weeks 0, 2, and 4. Replication allows us to assess if theta activity

changes during the study period. We will also explore other bandwidths (e.g., alpha, beta, delta, gamma) in our analysis. Medium or larger effect sizes for changes in bandwidth activity will be used to indicate that more formal testing in future research is warranted. *Explore the mediation effects of brain states (theta activity) on pain intensity at weeks 0, 2, and 4.* Cross-sectional analyses will examine mediation at weeks 0, 2, and 4 for how RHI and theta activity jointly affect pain intensity. The mediating effects model implicit in **Figure 1** will be tested using multiple regression models. Effect sizes (Cohen's d) will be computed for looking at the biological mechanism in a larger, more definitive study. *Structured interviews.* Transcribed interview data will be organized in ATLAS.ti7 (Scientific Software Development, Berlin, Germany). Content analysis^{10,11} will be used to understand the barriers and facilitators associated with undergoing qEEG measurement and perceptions on how the intervention works to reduce pain.

In summary, this study is extremely important because it will provide scientific evidence on the efficacy of a symptom self-management intervention that cancer survivors can easily use to manage a distressing symptom. Furthermore, this study is innovative in that it will increase our understanding of how this intervention works and who will most likely experience pain reduction when using this low-cost, accessible, and convenient intervention.

References

1. Morgan AH & Hilgard JR. (1978). The Stanford Hypnotic Clinical Scale for adults. *The American Journal of Clinical Hypnosis*, 21, 134-47.
2. [name] M. (2011). *Hypnosis for chronic pain management: therapist guide*. Oxford University Press.

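### Aim 1 says it will learn whether 4 weeks rather than 2 is necessary, but plans no overall Week 2 arm difference, no Week 4-minus-Week 2 contrast and no rule for reading the diary plots

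*Combined protocol and SAP*

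**What the plan says.** Under Data Analysis, Aim 1, the specified test is an ANCOVA, adjusted for baseline and covariates including drug treatment, of whether mean pain intensity "at week 4 differs between the RHI and relaxation groups". It is repeated for the secondary outcomes. For the time course the text says "we will graphically describe trajectories of daily pain and anxiety at Weeks 0, 2, and 4, based on the Daily Diary". It then states that this approach will let the investigator understand "whether an increased dose of the intervention (i.e., 4 weeks vs. 2) is necessary to achieve significant reduction in pain intensity".

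Three other places bear on the question:

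- **Aim 2** writes out a regression for Week 2 pain with baseline pain, a psychological factor, RHI and their product, "where moderator effects will be indicated by the interaction term". Cohen's d is to be measured "for each of the levels of the moderator and compare them to determine the moderator effect".
- **Aim 3** covers pain through theta activity: "Cross-sectional analyses will examine mediation at weeks 0, 2, and 4 for how RHI and theta activity jointly affect pain intensity". This uses the qEEG subset ("The 20 participants undergoing qEEG", in the paragraph on participant payment), chosen for low or high suggestibility scores.
- **Intervention/Independent Variables** assigns both arms daily listening for 28 days in the same order: four recordings for 3 days each, then the participant's own choice.

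Tables 2a and 2b schedule PROMIS pain intensity at Weeks 0, 2 and 4, and the diary daily.

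**The concern.** A statement that 4 weeks is needed where 2 would not do is a claim about the difference between two time points, relative to control. Aim 1 provides inference at only one of them. The diary plots come with no estimate, interval or reading rule, so the conclusion would rest on visual impression or on an unplanned comparison of two p-values.

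The wording, which ties necessity to a significant reduction, invites the second route: significant at Week 4, not significant at Week 2, therefore 4 weeks is needed. That inference is unsound, because the two results can differ by chance when the effect is the same at both visits.

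The design adds a further limit. Nobody is randomised to stop at 14 days, so even a well-estimated change in the arm difference would not show what a 2-week course achieves by Week 4. At stake is a published statement about how long the intervention must be used, without a planned estimate of what Weeks 2 to 4 add over control.

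**Working it through.** **1. Does another aim supply the missing estimate?** The Aim 2 model has an RHI term at Week 2. With the product term present, that coefficient is the arm effect at a moderator value of zero. It is an overall effect only if the moderator is centred, which is not stated. The planned reading is the interaction and d by moderator level. Aim 3 concerns mediation in 20 people with extreme scores. Neither gives an overall Week 2 arm difference or compares Week 4 with Week 2.

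**2. Reproduce Table 1.** Inputs from Table 1: 50 per arm, 80% power, two-sided alpha 0.05, SD 1.0, 1.5 and 2.0. The Power Analysis section describes the SDs as "based on standard deviations observed in our prior research" and names no instrument. A two-sample noncentral t calculation with 98 df gives 0.566, 0.849 and 1.132, matching 0.57, 0.85 and 1.13. Table 1 therefore addresses a difference in means at one time point and says nothing about change between visits.

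**3. Precision of the missing contrast.** Assumptions not in the documents: equal SD at both visits, full data, and a Week 2 to Week 4 correlation rho of 0.3 to 0.9.

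SE = SD × √(2(1 − rho)) × √(2/50)

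Baseline adjustment leaves this unchanged if baseline correlates equally with both visits. At rho = 0.5, SE = 1 × 1 × 0.200 = 0.200 SD. The half-width is 1.96 × 0.200 = 0.392 SD. The difference detectable with 80% power is 0.566 × √(2(1 − rho)) = 0.566 SD. The last column is power for a later gain of half the Table 1 effect, 0.566/2 = 0.283 SD.

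| rho | SE (SD) | 95% half-width (SD) | Detectable (SD) | Ratio to 0.566 | Power, half effect |
|---|---|---|---|---|---|
| 0.3 | 0.237 | 0.464 | 0.670 | 1.18 | 22% |
| 0.5 | 0.200 | 0.392 | 0.566 | 1.00 | 29% |
| 0.7 | 0.155 | 0.304 | 0.438 | 0.77 | 44% |
| 0.8 | 0.126 | 0.248 | 0.358 | 0.63 | 60% |
| 0.9 | 0.089 | 0.175 | 0.253 | 0.45 | 88% |

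At Table 1's expected SD of 1.5, half-widths are 0.70, 0.59, 0.46, 0.37 and 0.26, and detectable differences are 1.00, 0.85, 0.66, 0.54 and 0.38, against 0.85. SD units are the safer scale, since Table 1 does not name its instrument.

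**4. How often would comparing p-values mislead?** Suppose the true effect is 0.85 at both visits with SD 1.5, so that each test has 80% power, and the two test statistics correlate at rho. Then P(significant at Week 4, not at Week 2) = 0.80 − P(significant at both). By the bivariate normal this is 13.4%, 11.3%, 8.7% and 7.1% for rho = 0.3, 0.5, 0.7 and 0.8. In those trials 4 weeks would look necessary although nothing changed after Week 2.

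**5. Timing and content of the second half.** Fixed recordings cover 4 × 3 = 12 days, leaving 28 − 12 = 16 self-chosen days in both arms. Week 2 and Week 4 measures may be taken within 5 days of 14 and 28 days of use (Week 0 Study Visit). If the window runs afterwards, the visits fall on days 14–19 and 28–33, a gap of 28 − 19 = 9 to 33 − 14 = 19 days. If it runs both ways, they fall on days 9–19 and 23–33, a gap of 23 − 19 = 4 to 33 − 9 = 24 days.

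**The case against.** The strongest reply is that this is one interpretive sentence attached to an analysis labelled as graphical description. Aim 1's objective is efficacy at 4 weeks, and neither the sample size nor the primary test depends on the sentence. That is true, and it limits the weight of the point. But the sentence speaks of necessity and of significant reduction, which is not descriptive language. Following it as written would produce an unsupported conclusion rather than merely leave out a detail.

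Second, the precision figures describe a proposed contrast, not harm done by the plan, and they depend on a correlation the documents do not give. This stands: they are an illustration over a range. Their use is to show that an interval is needed. Half-widths based on t with 98 df rather than 1.96 would be slightly wider (0.470 instead of 0.464 at the upper end), which changes nothing.

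Third, a Week 4-minus-Week 2 contrast does not make the design able to show necessity. This also stands, so the contrast must be accompanied by rewording.

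Fourth, Aim 2's stated scope covers pain at Weeks 0, 2 and 4 in the whole sample, so some between-arm information at Week 2 is planned. It is, but by moderator level, with no overall estimate and no comparison over time.

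Finally, self-chosen recordings are the same in both arms and do not bias the arm comparison. They only limit attributing a later change to duration alone.

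**Conclusion.** The concern holds. The plan states a duration inference that no specified analysis supports and that the design, with both arms assigned 28 days, cannot deliver as worded. It should be corrected, but it does not threaten the primary Week 4 comparison.

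Under the stated assumptions, the between-arm change from Week 2 to Week 4 needs to be 0.25 to 0.67 SD to be detected with 80% power, or 45% to 118% of the Table 1 effect. A modest later gain may not be reliably distinguished from none unless the correlation between visits is high. Missing data would widen the intervals; the documents give no dropout rate. That the analysis and the rule are missing rests on the text alone and needs none of these assumptions.

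**What to change.** Keep the Week 4 ANCOVA as primary and the diary plots as description. Add two secondary analyses of PROMIS pain intensity, for example from one arm-by-visit repeated-measures model:

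1. the baseline-adjusted arm difference at Week 2, with a 95% confidence interval;
2. the between-arm Week 4-minus-Week 2 contrast, with a 95% confidence interval.

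Base any statement about duration on the contrast and its interval, not on the plots or on two p-values set side by side. Reword the sentence to speak of additional between-arm benefit between Weeks 2 and 4. State as limits that recordings are self-chosen in this period and that the visit window allows the gap to vary; also say in which direction the window runs.

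As a sensitivity analysis for the window, estimate the same contrast from diary pain at fixed days of use, for example the mean of days 8–14 against days 22–28. This changes the instrument and the averaging period as well as the timing, so a discrepancy could not be put down to the window alone.

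If no contrast is added, limit the sentence to saying that the plots describe the time course.

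The cost is SAP wording, one routine secondary model and one diary analysis, all on data already collected. The duration statement becomes more modest and may prove inconclusive at this sample size.

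### Aim 2 adds to its interaction test a second moderation criterion, a comparison of Cohen's d across undefined moderator levels with no interval or test, and uses the resulting effect size to size the follow-up study

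*Combined protocol and SAP*

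**What the plan says.** The Data Analysis section, Aim 2, names three moderators: "hypnotic suggestibility, mental absorption, treatment outcome expectancy". Each enters a regression of pain on baseline pain, the moderator, treatment group and their product. The text under the equation states that "moderator effects will be indicated by the interaction term".

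The next sentence has Cohen's d measured at each level of the moderator, the purpose being to "compare them to determine the moderator effect". The one after that reads: "The resulting effect size will be used to estimate the sample size in a larger follow-up study".

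The plan does not say what the levels are, which of the two criteria prevails if they disagree, or which effect size is carried forward. It attaches no interval, test or threshold to the comparison of d values. Table 1 gives detectable differences for the comparison of the two groups only ("For N=100 (50/group), 80% power, alpha = 0.05, two-sided"). Nothing comparable is given for Aim 2.

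**The concern.** An interaction test has a known error rate. A visual comparison of several d values does not, and with 100 participants each level-specific d comes from a small part of the sample. The d values will differ even if hypnosis works equally well for everyone, and the more levels there are, the wider the spread between the extremes.

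Two things are at stake. The trial could report that the recordings work for some survivors and not for others on the strength of a chance gap. That gap could then be taken as the effect to be detected in the next study, which would be too small because an overstated effect needs fewer participants.

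**Working it through.** **Inputs.** Table 1: 50 per group, "80% power, alpha = 0.05, two-sided", standard deviations 1.0, 1.5 and 2.0, detectable changes 0.57, 0.85 and 1.13 in absolute value. Table 2b: "Stanford Hypnotic Clinical Scale for Adults 5-item scale", so total scores run from 0 to 5 and there are six possible values. The Design paragraph labels 0–1 low and 4–5 high, but only to select participants for qEEG.

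**Step 1: the plan's own figure.** The normal approximation is (1.96 + 0.84) × SD × √(2/50) = 0.56 × SD, giving 0.560, 0.841 and 1.121 (unrounded z values). The t-based solution with 98 degrees of freedom gives 0.566, 0.849 and 1.132. Table 1 reproduces. It corresponds to a d of about 0.57, used below as the common true effect.

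**Step 2: participants per arm per level.** The plan states none. Assuming even filling and no dropout: six scores, 50/6 = 8.3 (8 used); three bands, 50/3 = 16.7 (17 used); median split, 50/2 = 25.

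**Step 3: precision.** With n per arm per level, SE(d) = √(2/n + d²/(4n)), and the gap between two levels has SE = √2 × SE(d). For n = 8: √(0.250 + 0.010) = 0.51, and √2 × 0.51 = 0.72. For n = 17: 0.35 and 0.49. For n = 25: 0.29 and 0.41.

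**Step 4: gaps that arise by chance.** Trials were simulated with normal data, equal SDs, no variance reduction from baseline and a true d of 0.57 at every level. Repeated runs agree to about one percentage point.

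| Levels | n per arm per level | Largest minus smallest > 0.5 | Same, > 0.8 | Two end levels only, > 0.5 | Same, > 0.8 |
|---|---|---|---|---|---|
| Six scores | 8 | 98% | 89% | 51% | 29% |
| Three bands | 17 | 58–59% | 26% | 32–33% | 12% |
| Median split | 25 | 23% | 5–6% | 23% | 5–6% |

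Hand check for two end levels with n = 8: 0.5/0.72 = 0.69, two-sided normal tail about 49%, against 51% simulated. A true d of 0 gives nearly the same results. Uneven filling of the six scores raises the median largest-minus-smallest gap from 1.34 to between 1.39 and 1.47.

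**Step 5: the interaction test.** With no moderation, it rejected in 4% to 5% of simulated trials at a nominal 5%. For a continuous moderator in SD units, the interaction has SE of about √(4/100) = 0.20, so its 95% half-width is 1.96 × 0.20 = 0.39 d per SD. The detectable interaction at 80% power is 2.80 × 0.20 = 0.56 d per SD.

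**Step 6: sensitivity of a follow-up, as illustration only.** For a 2×2 interaction, total N = 16 × (1.96 + 0.84)²/gap². A gap of 0.5 gives 16 × 7.85/0.25 ≈ 502; a gap of 0.8 gives 16 × 7.85/0.64 ≈ 196. Rounding up within each of four cells gives 504 and 200.

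**The case against.** The strongest reply is that the plan already contains the right test. The interaction sentence comes first, and the sentence on d can be read as quantifying a moderator effect once the interaction has indicated it, which is the usual order of testing and then probing. The regression uses a single term for each moderator, which is consistent with a continuous score, and the d values could come from that model at chosen moderator values. This stands in part: a valid test is planned, and the verb in "compare them to determine the moderator effect" is ambiguous. But the text does not make the comparison conditional on the interaction, attaches no uncertainty to it, and gives the resulting effect size a definite use. Even d values taken from the model at +1 and −1 SD differ by more than 0.5 in about 23% of trials without moderation, so the missing interval matters on that reading too.

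A reader might also infer more than the documents support:

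- **That cells of about 8 are planned and 89% of trials would mislead.** The plan sets no levels or cell sizes. Eight applies to one of three moderators, with all six scores used and evenly filled, and 89% also requires comparing the extreme d values. Other readings give 5% to 29% for a gap above 0.8.
- **That cut-points are unavoidable for absorption and expectancy.** Model-based effects need none.
- **That the follow-up will be undersized by a known amount.** The plan does not say which effect size or test it would use. The figures of about 500 and 200 show sensitivity only.

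**Conclusion.** The concern holds in a limited form. Aim 2 has a valid indicator of moderation and, beside it, a second criterion without interval, test or defined levels, whose result is to inform the next sample size. How badly that second criterion behaves depends on choices the plan leaves open: with no moderation at all, a largest-minus-smallest gap above 0.5 appears in anything from 23% of trials (median split) to 98% (six scores). Even the most favourable of these is well above the 5% of the interaction test.

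The figures assume even filling, no dropout, equal SDs, no gain from baseline adjustment and a common true d of 0.57. Dropout would make the gaps larger; variance explained by baseline would improve the precision of the interaction estimate. The Aim 1 comparison of pain intensity at week 4 does not depend on any of this.

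**What to change.** In Aim 2:

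1. State that moderation is judged only from the product-term coefficient with its 95% confidence interval, each moderator entered as a continuous, centred score.
2. Replace the level-by-level comparison of d with model-based treatment effects at the moderator's mean and ±1 SD, each with a 95% confidence interval and labelled descriptive.
3. State that follow-up planning will use the confidence interval of the interaction, not a point difference in d.

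The regression is already planned, so this changes wording only and needs no new data. The cost is a wider and less striking result: at this size the interval will be about ±0.39 d per SD of the moderator, and the report should say so.
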